1.4.2. Sample Size Estimation Comparing High versus Low Prophylactic Dosing

A secondary objective is to evaluate the effect of a high versus low dosing frequency schedule on prophylactic efficacy. Data from the previously mentioned moroctocog alfa study 301 revealed an ABR of 5.7 ± 5.2 (N=26) in subjects receiving a high-frequency prophylaxis regimen (3 infusions per week) compared to an ABR of 7.1 ± 4.1 (N=13) in patients receiving a lower-frequency prophylaxis regimen (2 infusions per week). Assuming an intraclass correlation of 30% and a standard deviation of 6 bleeds per year based on the above study results, a within-subject standard deviation of 5 bleeds per year was used for sample size calculations for the comparison between the high- and low-frequency prophylaxis regimens. Given this, 36 RP subjects are needed to provide 80% power to demonstrate equivalence of the two regimens. The two regimens will be considered equivalent if the limits of the 90% two-sided confidence interval for the difference in observed mean ABRs falls wholly within the interval of -4 to 4 bleeds per year. Allowing for an attrition rate of 25%, approximately 48 RP subjects should be enrolled to support this objective.

Based on a sample size re-estimation using data from this ongoing study, a difference of means of 1.3 bleeds per year between the two protocol-defined prophylaxis regimens (A and B) with a corresponding standard deviation of the difference of 6.5 was obtained requiring 38 subjects to provide 80% power to demonstrate equivalence of the two regimens. Allowing for an attrition rate of 30%, approximately 56 RP subjects need to be enrolled. The two prophylaxis regimens will be considered equivalent if the limits of the 2-sided 90% confidence interval for the difference in observed mean ABRs fall wholly within the interval defined by fewer than 4 bleeds per year. See the Summary of Changes to Planned Analyses for the Final CSR (Item 4) for further discussion.

1.4.3. Sample Size for Pharmacokinetic Assessments

Not applicable.

1.5. Description of Planned Study Implementation and Procedures

Three study flowcharts including procedures across the length of the study can be found in the protocol.

1.6. Blinding

This study is entirely open-label and does not necessitate any blinding.

2. ANALYSIS OF PHARMACOKINETIC ENDPOINTS

A subset of study subjects will participate in a single PK assessment at the start of the study. For the assessment, the response to a single 50 ± 5 IU/kg infusion of moroctocog alfa (AF-CC) will be evaluated. The PK assessment will occur at the beginning of the study (visit 2), before subjects initiate moroctocog alfa (AF-CC) treatment. The assessment will permit characterization of the single-dose PK properties of moroctocog alfa (AF-CC) at initial exposure.

2.1. Pharmacokinetic Endpoints

The primary PK variables will be terminal phase half-life $(t_{1/2})$, incremental recovery (K-value), and clearance (CL). Secondary PK variables will include: maximum concentration (FVIII:C at 0.5 hours after study drug infusion $[C_{0.5 \text{ hr}}]$), area under the curve to infinity (AUC $_{\infty}$), area under the curve to last measurable concentration (AUC $_{v}$), steady-state volume of distribution (V_{SS}), and mean residence time (MRT).

Summaries for each of these variables will be reported for the PK assessment to characterize the single-dose PK of moroctocog alfa (AF-CC) at initial exposure.

2.2. Actual Dose Calculation

A single bolus of study drug at a dosage of 50 ± 5 IU/kg will be administered for the PK assessment. The dose, prepared from a single lot, will be calculated based on the labeled actual potency of the study drug and the subject's actual body weight as measured on the day of study drug administration and will be documented. See Summary of Changes to Planned Analyses for the Final CSR (Item 7) for further discussion.

2.3. Analysis Populations

2.3.1. Evaluable Populations

PK subjects must meet the additional PK eligibility criteria, including $\leq 1\%$ FVIII activity at screening (by central laboratory), and < 16 years of age at the time of visit 2 for this analysis.

The primary analysis for PK characterization of moroctocog alfa (AF-CC) will be performed on the per-protocol population.

For the analysis of single-dose PK, this population (herein referred to as the PK-evaluable population) consists of subjects who have no major protocol violations, who supply adequate sampling for the PK assessment while in a nonbleeding state, who had adequate FVIII washout, and who do not have a confirmed FVIII inhibitor at the time of the assessment.

A \geq 72-hour washout of FVIII activity is required before all infusions. A subject with \leq 72 hour washout of FVIII prior to PK testing may be included for the baseline assessment, if it is determined that he had negative FVIII inhibitor value and the baseline FVIII activity (T=0 pre-infusion level) \leq 1%, before the infusion. However, this might constitute a protocol deviation and a scientific judgment should be provided for inclusion of each such subject.

If subjects are missing measurements necessary for the calculation of certain summary statistics, their data will not be used in the calculation of that statistic. However, this does not preclude the use of their data for other statistics. The number and percentage of subjects that meet the criteria for the analysis population will be summarized by treatment regimen.

2.4. Data Preparation

The sampling times that will be used in the PK calculation will be the actual sampling time recorded relative to the time of dose administration.

2.5. Analysis Methods

The factor VIII activity pharmacokinetic parameters for each PK subject will be derived from the plasma FVIII activity time data at the beginning of the study (visit 2), based on non-compartmental (NCA) methods, as specified in the protocol.

All PK variables will be summarized by descriptive statistics (n, mean, median, standard deviation (SD), standard error (SE), minimum and maximum, coefficient of variance % (CV), geometric mean, and 95% confidence interval (CI)).

2.6. Statistical Software

An internally developed and validated software system, eNCA version 2.2.4, or current version-will be used to perform PK analysis and statistical comparisons on PK parameters.

3. ANALYSIS OF SAFETY AND EFFICACY ENDPOINTS

All data collected during the course of the study will be presented in a listing format.

In general, descriptive statistics will summarize all efficacy and safety endpoints as appropriate. For continuous variables, number, mean, standard deviation, median, minimum, and maximum will be provided. Interquartile ranges and 95% confidence intervals may be provided where meaningful. For categorical variables, frequency and percentage will be presented for each category.

Safety and efficacy analyses for the OD subject cohort (on-demand therapy in segment 1, followed by the prescribed prophylaxis regimen in segment 2), will be done independently from the analyses for the RP subject cohort (randomized to follow prophylaxis regimens in both segments 1 and 2). PK characterization will be presented for all subjects (in either cohort) who provided PK data. In addition, select tables will be provided for all subjects in the study, regardless of cohort. See Summary of Changes to Planned Analyses for the Final CSR (Item 8) for further discussion.

3.1. Baseline Demographics and Treatment Characteristics

The mean, median, standard deviation, minimum, and maximum will be reported for age (years or months, as appropriate), weight (kilograms), and height (centimeters). Number and percentage will be used to describe sex, race, ethnicity, and hemophilia severity. A summary of subject disposition (eg, completed the study, or discontinuation reasons) and time on study will be provided.

3.2. Analysis Populations

3.2.1. Intent-to-Treat Populations

The intent-to-treat (ITT) population includes all subjects for whom a legal acceptable representative has signed the informed consent/assent form. Screen failures will not be included in the ITT population. All safety and efficacy analyses will be performed on the ITT population.

The modified Intent-to-Treat (mITT) population is the subset of ITT subjects who received at least one dose of moroctocog alfa (AF-CC). Adverse events and lab data analyses will be additionally performed on the mITT population. Analysis of the incidence of confirmed FVIII inhibitor development will also be performed on the mITT population.

3.2.2. Per-Protocol Populations

Efficacy analyses will also be performed on per-protocol populations.

3.2.2.1. Prophylaxis to On-Demand Per-Protocol Population

For the analysis comparing moroctocog alfa (AF-CC) prophylaxis to on-demand treatment, the per protocol population (herein referred to as the PR-OD population) consists of the subset of OD subjects who have no major protocol violations (see SAP Section 3.7.1), who practice on-demand treatment exclusively during study segment 1, and who practice prophylaxis during study segment 2. An interruption in treatment due to any unplanned and required surgery will not necessarily disqualify the subject from the PR-OD population, but the time on surgery will not count towards time on treatment in either segment. If a subject requires a dose escalation, only the data from the time on the originally prescribed regimen will be used for segment 2. The first month of segment 2 prophylaxis will be considered a washout period. Analyses will be performed with and without data from the washout period in order to assess and minimize the effect of the previous treatment regimen on ABR. Note: If an OD subject develops a confirmed FVIII inhibitor, his data will be included up to the time an inhibitor is determined to be present.

3.2.2.2. Prophylaxis Regimens Per-Protocol Population

For the analysis comparing the two moroctocog alfa (AF-CC) prophylaxis regimens (A and B), the per-protocol population (herein referred to as the PR_A-PR_B population) consists of the subset of RP subjects who have no major protocol violations (see SAP Section 3.7.1) and who practice protocol-defined prophylaxis during segment 1 and during segment 2. An interruption in treatment due to any unplanned and required surgery will not necessarily disqualify the subject from the PR_A-PR_B population, but the time on surgery will not count towards the time on treatment in either segment. If a subject requires a dose escalation, only

the data from the time on the originally prescribed regimen will be used. The first month of each segment will be considered a washout period. Analyses will be performed with and without data from the washout periods in order to assess and minimize the effect of the previous treatment regimen on ABR. Note: If a RP subject develops a confirmed FVIII inhibitor, his data will be included up to the time an inhibitor is determined to be present.

3.2.2.3. Efficacy Evaluable Population

For the descriptive analysis of moroctocog alfa (AF-CC) efficacy over the entire course of the study, the per-protocol population (herein referred to as the efficacy-evaluable population) consists of all OD and RP subjects who have no major protocol violations (see SAP Section 3.7.1), and who accrue \geq 50 exposure days and/or receive moroctocog alfa (AF-CC) treatment for \geq 6 months in the study.

3.3. Efficacy Endpoints

The efficacy analysis to test the primary objective of comparing ABRs while on on-demand therapy versus prophylaxis will be performed on the ITT population. Supportive analyses will also be run on the PR-OD population. The efficacy analysis to test the secondary objective of comparing ABRs while on high- versus low-frequency prophylaxis will be performed on the ITT population. Supportive analyses will also be run on the PR_A-PR_B population. All other efficacy analyses will be performed on the ITT and efficacy-evaluable population. Analyses will be adjusted for the two stratification factors of prophylaxis treatment regimen (A and B) and hemophilia severity, as appropriate.

For efficacy analyses, dose calculations will be based on the actual potency rather than the target potency. For example, an infusion of 2 vials of lot 1 with a target potency of 2000 IU each and an actual potency of 1975 IU is an actual dose of 3950 IU. Dose (IU/kg) is calculated by dividing the subject's administered dose (IU) by the subject's weight (kg) taken from the most recent visit within 3 months preceding the infusion. If this weight is missing, the weight will be taken from the most recent visit within 3 months following the infusion. If no weight is available within 3 months, the dose will be calculated based on the last available weight and it will be noted that weight was not measured within 3 months of the infusion.

Bleeds treated with study drug will be included in efficacy analyses. If FVIII replacement products, other than study drug, are used, the infusion will be counted in the number of infusions needed to treat the bleed and noted. Bleeds that do not require FVIII treatment (such as bruises, hematoma, hematuria, epistaxis) will be listed separately and not included in efficacy analyses.

Bleed locations are categorized as joint, soft tissue/muscle, or other when reported. Bleeds that occur at more than one site (eg, both elbows, hand and knee, or joint and soft tissue) will be classified into a 'multiple sites' category. Bleeds that occurred at a site that cannot be classified as joint or soft tissue/muscle, eg, hematuria, or if the bleed site is unknown or missing, will be classified into 'other' category.

Efficacy data on and subsequent to the date of inhibitor development will not be included in efficacy analyses. The date of inhibitor development is the date that the blood sample was drawn for the positive Factor VIII inhibitor assay (by the Nijmegen method) or the SAE date reported by the investigator on the AE screen, whichever is earlier.

A summary for each bleeding episode by subject, with type of bleed (spontaneous or traumatic), number of infusions needed to resolve the bleed, mean dose, total dose and response, will be provided. A subject-based analysis of total number of bleeds (spontaneous and traumatic), total number of infusions and total dose needed to treat bleeds will also be provided by subject group (OD subjects and RP subjects).

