## 18.1.2. Location of Bleeds

For the purposes of this study, when subjects report a bleed treated with study drug, the location of the bleed should be recorded in the Subject Diary or medical record. Bleeds will be reported as occurring in 1 of the following locations: joint, muscle/soft tissue, or other. Each individual location of multiple-site bleeds will be reported. For joint bleeds, the specific joint will be reported. Parameters to identify joint bleeds include: pain on joint motion, limitation of motion, and visible swelling of joint.

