3.3.1.2. Analysis Method

The null hypothesis is that prophylactic treatment does not reduce the ABR relative to ondemand treatment. The alternative hypothesis is that prophylactic therapy results in a reduction in ABR.

An analysis of variance (ANOVA) will be conducted to compare the mean ABR between subjects in on-demand (segment 1) and prophylaxis (segment 2) treatment regimens. The ANOVA will include factors for treatment regimen (study segment 1 or 2) and a blocking factor for hemophilia severity (<1% and [1%, 2%]). The model will also include a blocking factor for subject to ensure that the comparison of ABRs from each treatment regimen is performed on a within subject basis. The p-value for treatment regimen calculated for ABR of the ITT population will be used to test the null hypothesis; a p-value less than 0.05 will be considered statistically significant. See Summary of Changes to Planned Analyses for the Final CSR (Item 2) for further discussion.

Additionally, ABR will be presented as descriptive statistics (n, mean, SD, median, interquartile range, minimum, and maximum). ABRs will be summarized by bleed type (ie, spontaneous or traumatic), by bleed location (eg, joint, soft tissue/muscle), and by treatment (ie, segment 1, segment 2).

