3.3.2.1. Variable Definition

To assess the efficacy of routine prophylaxis, the ABR will be derived for each subject for each prophylaxis regimen by using the following formula:

ABR = number of bleeds / (Days on treatment regimen/365.25)

The number of bleeds for the ABR calculation includes all bleeds requiring treatment with a FVIII replacement product during the time on treatment. For segment 1 prophylaxis, days on treatment regimen for this calculation is defined as (date of visit 11 – date of visit 2) +1. For segment 2 prophylaxis, days on treatment regimen for this calculation is defined as (date of visit 19 – date of visit 11). If a subject does not complete a study segment, the days on treatment ends at the last study visit. The ABR will be calculated 3 ways: 1) including all data from the ITT population (all RP subjects), 2) including all data from the PR_A-PR_B population and 3) including all data from the PR_A-PR_B population except the first month of each segment (considering the first month to be a washout period and allowing for an analysis of the sensitivity of ABRs to previous therapy).

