3.3.2.2. Analysis Method

The null hypothesis is that there is a difference in ABR between the two prophylaxis regimens. The alternative hypothesis is that the two prophylaxis regimens are similar enough to be considered clinically equivalent.

The 90% 2-sided confidence interval (CI) for the mean difference in ABRs for the 2 prophylaxis regimens for ITT subjects will be constructed using the t distribution with n-1 degrees of freedom (n equals the number of subjects) to assess the equivalence of these 2 regimens. Equivalence will be demonstrated and the null hypothesis rejected if the limits of the 90% CI fall wholly within the interval of (-4, 4) bleeds per year. See Summary of Changes to Planned Analyses for the Final CSR (Item 4) for further discussion.

Additionally, an ANOVA model appropriate for the crossover design will be employed to test for the presence of treatment sequence, period and carryover effects. The ANOVA model will be fitted with terms for treatment sequence (AB or BA), treatment frequency (A or B), period (study segment 1 or 2), carryover and subject nested in treatment sequence. If one or more of the terms for treatment sequence, period or carryover are statistically significant then exploratory analyses may be prepared to help understand the nature of the effect. See Summary of Changes to Planned Analyses for the Final CSR (Item 6) for further discussion.

ABR will also be presented as descriptive statistics (n, mean, SD, median, interquartile range, minimum, and maximum). ABRs will be summarized by bleed type (ie, spontaneous or traumatic), by bleed location (eg, joint, soft tissue/muscle), and by treatment frequency (ie, prophylaxis A, prophylaxis B).

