3.3.3.6. Consumption of Moroctocog Alfa (AF-CC)

For consumption of moroctocog alfa (AF-CC) per bleed, the dose for the first infusion (IU/kg) and the total dose (IU/kg) administered for the bleed will be summarized by bleed location (joint, soft tissue/muscle, multiple sites, and other). For consumption of moroctocog alfa (AF-CC) over time, the total IU, the number of infusions, exposure days (ED), and dose (IU/kg and IU) per infusion will be summarized by reason of dosing (ie, on-demand or prophylaxis).

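### The SAP's by-location joint ABR counts single-site joint bleeds only, because every bleed at more than one site, even one confined to joints, is classified as multiple sites

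*SAP*

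**What the plan says.** SAP 3.3 sets three base locations: "Bleed locations are categorized as joint, soft tissue/muscle, or other when reported". It then adds a fourth for bleeds at more than one site and gives examples: "eg, both elbows, hand and knee, or joint and soft tissue) will be classified into a 'multiple sites' category". The first example is confined to joints, and the last contains a joint by its own wording.

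The ABR is then broken down by location in both cohorts. For the on-demand (OD) cohort, SAP 3.3.1.2 summarizes it "by bleed location (eg, joint, soft tissue/muscle), and by treatment (ie, segment 1, segment 2"). For the routine prophylaxis (RP) cohort, SAP 3.3.2.2 does so "by bleed location (eg, joint, soft tissue/muscle), and by treatment frequency (ie, prophylaxis A, prophylaxis B"). Neither section gives joint a different meaning or returns multi-site joint bleeds to the joint row.

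The consumption tables in SAP 3.3.3.6 show that the categories are meant to exclude one another, since consumption is "summarized by bleed location (joint, soft tissue/muscle, multiple sites, and other"). Protocol 22.5.3 uses the same four-way split.

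On data collection, Protocol 18.1.2 states: "Each individual location of multiple-site bleeds will be reported". It adds: "For joint bleeds, the specific joint will be reported".

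The total ABR does not depend on location: "The number of bleeds for the ABR calculation includes all bleeds requiring treatment with a FVIII replacement product during the time on treatment" (SAP 3.3.2.1; SAP 3.3.1.1 uses the same numerator for the OD cohort).

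**The concern.** Most readers would take a row labelled joint ABR as the rate at which bleeds occur in joints. Under the SAP's rule, a child who bleeds into both elbows and is treated adds nothing to that row. Nor does a child with a knee bleed that extends to soft tissue. The bleeds left out are those at several sites.

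Joint bleeding matters in this protocol. Prophylaxis is defined by the prevention of spontaneous musculoskeletal bleeds (Protocol 4), and better joint integrity is among the reasons given for it (Protocol 9.4). The joint row is therefore likely to be read and cited on its own. What is at stake is whether that descriptive figure is complete and clearly labelled.

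**Working it through.** The documents state no joint ABR and no share of multi-site bleeds, so there is no figure to reproduce. The check traces the rule and then sizes the gap under stated assumptions.

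**Inputs**
- Classification rule: SAP 3.3.
- T, total ABR: 6.15 per year on prophylaxis and 11.85 on demand, from the previous pediatric study cited in SAP 1.4.1. Used for scale only.
- j, share of treated bleeds at a single joint site: assumed 40%, 50% or 60%.
- m, share of treated bleeds that are multi-site with at least one joint: assumed 0% to 20%. Multi-site bleeds that involve no joint do not enter m.

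**Formulas**
- Joint ABR under the SAP = T × j
- ABR for any joint involvement = T × (j + m)
- Relative shortfall = m / (j + m), which does not depend on T

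The direction follows from the rule: T × j cannot exceed T × (j + m), and the two are equal only when m = 0.

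**One case in full** (T = 6.15, j = 50%, m = 10%): the SAP row is 6.15 × 0.50 = 3.08; the any-joint rate is 6.15 × 0.60 = 3.69; the gap is 0.62 bleeds per year, and 0.10 / 0.60 = 16.7%.

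**Relative shortfall over the assumed range**

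| j | m = 0% | m = 2% | m = 5% | m = 10% | m = 20% |
|---|---|---|---|---|---|
| 40% | 0% | 4.8% | 11.1% | 20.0% | 33.3% |
| 50% | 0% | 3.8% | 9.1% | 16.7% | 28.6% |
| 60% | 0% | 3.2% | 7.7% | 14.3% | 25.0% |

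**Effect on a contrast.** The SAP row divided by the any-joint rate is j / (j + m) = 1 / (1 + m/j).
- If m/j is the same under both treatments, the ratio of joint ABRs is unchanged. The absolute difference shrinks by the shortfall in the table.
- If m/j differs, the ratio moves. Take j = 50% on both, m = 10% on demand and m = 5% on prophylaxis. The SAP rows are 11.85 × 0.50 = 5.925 and 6.15 × 0.50 = 3.075, a reduction of 48.1%. The any-joint rates are 11.85 × 0.60 = 7.11 and 6.15 × 0.55 = 3.3825, a reduction of 52.4%. With these assumed values the benefit of prophylaxis is understated.

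**Scale in the OD cohort.** SAP Appendix C reports 8 subjects with both regimens at the second interim report. Among 8 subjects with complete segments, one reclassified bleed changes the mean joint ABR by 1 / 0.5 / 8 = 0.25 per year in a 6-month segment, or 1 / 1 / 8 = 0.125 in a 12-month segment.

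**The case against.** The strongest reply is that this is a choice of definition, not a contradiction. Neither document defines the joint ABR as any bleed with a joint site. Exclusive categories count each bleed once, make the location rows add up to the total, and agree with the protocol's own consumption table. That stands, and it is why the exclusive breakdown should stay.

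It can also be said that nothing is lost. The location lists for ABR are introduced as examples, so a multiple-sites row may be shown, and SAP 3 presents all collected data in listings. This stands in part. Such a row would mix bleeds that involve a joint with bleeds that do not, so the joint rate could not be recovered from the table. A reader would have to rebuild it from listings.

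Three stronger readings are tempting, and the documents support none of them.
- A reader might infer that the efficacy conclusions are biased. The primary comparison and the equivalence interval use total ABR, which counts treated bleeds at any site. ABR by location is descriptive, and joint ABR is neither an objective nor a separately listed efficacy variable.
- A reader might infer that the rule touches escalation or target-joint status. Those follow the definitions in Protocol 15.3.3 and Protocol 4 and do not use the SAP's reporting category.
- A reader might infer that the treatment contrast is distorted, or distorted in favor of prophylaxis. Distortion of the ratio needs unequal multi-site shares, about which the documents say nothing. In the intuitive case, with relatively more multi-site joint bleeds on demand, prophylaxis would look less beneficial, not more. For A versus B there is no stated reason to expect a difference.

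**Conclusion.** The point holds as a matter of completeness and labelling in a descriptive table. Followed as written, the SAP reports single-site joint bleeds under the name joint, and that rate is lower than the rate of bleeds involving a joint whenever at least one treated multi-site bleed includes a joint.

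The direction is certain, but the size is not known. The range of about 3% to 33% rests entirely on assumed shares (j from 40% to 60%, m from 2% to 20%), and the shortfall is zero if m is zero. No hypothesis test changes. This is a cheap improvement, not a flaw that threatens the trial's conclusions.

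**What to change.** In SAP 3.3.1.2 and 3.3.2.2, add one row to the by-location ABR summary and relabel another:

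- **Any joint involvement:** treated bleeds with at least one joint site, each episode counted once (a bleed in both elbows is one bleed), derived from the individual sites recorded under Protocol 18.1.2.
- **Single-site joint:** the new label for the existing joint row.

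Keep the exclusive categories of SAP 3.3, including multiple sites, for the location breakdown and the per-bleed tables. Footnote that the any-joint row overlaps the exclusive rows and is not part of their sum. Total ABR is unchanged, with each bleed counted once.

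The cost is a short SAP wording change, minor programming and one overlapping row. No new data are needed.

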## 22.5. Analysis of Study Variables

## **22.5.1.** General

A discussion of the statistical methods by which the study hypotheses will be tested is provided below (see section 22.5.3). In addition, continuous variables for PK, efficacy, and safety analyses will be summarized by descriptive statistics. Categorical variables will be presented in frequency tables, with counts and percentages provided for each category. Missing data will be reported as such and no imputation will be made. Additional details of the study analyses will be provided in the statistical analysis plan.

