3.5. Missing Data

Missing data will be reported as such and no imputation will be made unless otherwise specified. The proportion of data that is missing for key variables will be presented if appropriate. The study will diligently collect all the data as planned. If any pattern of missing data is identified, extra effort will be made to ensure that the analysis is not affected by the circumstances.

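### SAP 3.3 codes treated bleeds with an unknown or missing site as location 'other', so the descriptive 'other' rows mix real sites with blanks and the number of missing sites is not shown

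*SAP*

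**What the plan says.** Protocol 18.1.2 asks that, for each bleed treated with study drug, "the location of the bleed should be recorded in the Subject Diary or medical record". It gives three levels: "Bleeds will be reported as occurring in 1 of the following locations: joint, muscle/soft tissue, or other". There is no level for an unknown site, so 'other' is a substantive answer, meaning a site that is neither joint nor muscle/soft tissue.

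SAP 3.3 uses the same three levels, adds a 'multiple sites' category, and then widens 'other'. A bleed at a site that is neither joint nor soft tissue/muscle (hematuria is the example) goes there, "or if the bleed site is unknown or missing, will be classified into 'other' category".

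On missing data, protocol 22.5.1 states: "Missing data will be reported as such and no imputation will be made". SAP 3.5 softens this: "Missing data will be reported as such and no imputation will be made unless otherwise specified". It adds: "The proportion of data that is missing for key variables will be presented if appropriate". Bleed site is not named as a key variable.

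Location is a breakdown for:
- ABR in the OD cohort (SAP 3.3.1.2) and in the RP cohort (SAP 3.3.2.2, "by bleed location (eg, joint, soft tissue/muscle), and by treatment frequency");
- infusions per bleed (SAP 3.3.3.1);
- first-infusion response (SAP 3.3.3.2);
- consumption per bleed (SAP 3.3.3.6), where 'other' is named as a row.

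**The concern.** A recorded hematuria and a blank field receive the same code. The blank is then tabulated as a location instead of being reported as missing, which is what the protocol asks for. The eight items in the SAP's Summary of Changes to Planned Analyses for the Final CSR do not mention this.

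What is at stake is how the by-location tables read. An 'other' row that contains unrecorded joint or muscle bleeds misstates how often true other-site bleeds occur, how they respond and how much factor they use. A reader of the joint row also cannot see how many bleeds had no site, and so cannot judge how incomplete that row may be.

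**Working it through.** No figure in the plan depends on the location coding, so there is none to reproduce. The check is bookkeeping.

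**Inputs**
- p = true share of treated bleeds at 'other' sites. Assumed 5% or 10%; the documents give none.
- m = share of treated bleeds with no recorded site. Assumed 5% to 15%; the documents give none. Taken as unrelated to the true site.
- For an example in bleeds per year: total ABR 6.15, the prophylaxis figure from the previous ReFacto PUP study (protocol 22.7), with an assumed split of joint 60%, soft tissue 20%, multiple sites 10%, other 10%.

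**Reported 'other' share under SAP 3.3** = p(1 - m) + m

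| p | m = 5% | m = 15% |
|---|---|---|
| 5% | 0.05 × 0.95 + 0.05 = 9.8% | 0.05 × 0.85 + 0.15 = 19.3% |
| 10% | 0.10 × 0.95 + 0.05 = 14.5% | 0.10 × 0.85 + 0.15 = 23.5% |

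The reported share therefore runs from about 10% to about 24%. If missingness does depend on site, the excess lies between 0 (every blank was truly 'other') and m (none was).

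**Example at m = 10%, total ABR 6.15**
- True 'other': 0.10 × 6.15 = 0.615 per year.
- Unknown site: 0.10 × 6.15 = 0.615.
- Reported 'other' under the SAP: 0.615 × 0.90 + 0.615 = 1.169, which is 1.90 times the true rate. The ratio is 1.18 at m = 2% and 1.45 at m = 5%.
- Unrecorded joint bleeds inside that row: 0.60 × 0.615 = 0.369, or 0.369/1.169 = 32% of it.

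**The same data with a separate 'unknown/missing' row**
- 'Other': 0.615 × 0.90 = 0.554.
- Joint: 0.60 × 6.15 × 0.90 = 3.321. This is also the value under the SAP rule (true value 3.69).
- Total: 6.15 either way.
- New information: the joint share among known-site bleeds is 3.321/(6.15 × 0.90) = 60%, the true share. The joint rate is bounded by 3.321 (no unknown bleed was joint) and 3.321 + 0.615 = 3.936 (all were).

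So the coding changes the 'other' row only. A separate row leaves the joint count where it was but shows how far it could be off.

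**The case against.** Four things can be said for the plan.

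1. The protocol leaves analysis details, including those on missing data, to the SAP (protocol 22 and 22.5.1). SAP 3.5 allows exceptions and SAP 3.3 states one openly. This stands within the SAP: the rule is declared, and a reader of the SAP knows what the row contains. It does not remove the conflict with protocol 22.5.1, which has no exception clause, and a reader of the tables alone would not know.

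2. Few sites may be missing. Location is requested for every treated bleed, diaries are reviewed at each visit, monitors check the records for consistency, and automated checks trigger queries to the site (protocol 15.1, 18.1 and 32.2). This stands. If no site is missing, the rule has no effect.

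3. The raw record survives, because SAP section 3 lists all collected data. This is true, but a count would have to be made by hand. The per-bleed summary described in SAP 3.3 does not name location, and the missing proportion is promised only conditionally. The documents contain no table shells, so a footnote cannot be ruled out; none is specified.

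4. The affected tables are descriptive, and the ABR text names only joint and soft tissue/muscle as examples. This stands and limits the weight of the point.

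**Conclusion.** The point holds as a minor one. SAP 3.3 merges missing sites with a real location, contrary to protocol 22.5.1. If any sites are missing, the 'other' rows are inflated, unless every one of those bleeds truly was at an 'other' site. Under the assumed 5-15% missing and a true share of 5-10%, the reported share would be about 10-24%. These inputs are illustrative; the true size may be nil.

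A reader might infer that the rule understates joint and soft-tissue bleed rates, or could create a regimen difference: with 15% of sites missing on one regimen and 5% on the other, joint rates would stand in the ratio 0.85/0.95 = 0.895, about 11% apart. The documents do not support blaming the coding for this. A bleed with no recorded site is not counted as joint under either label, so both effects would come from the missing record itself. Nothing in the documents suggests that recording differs by regimen. The separate SAP rule that moves multiple-site bleeds (two elbows, for example) out of the joint row is a different matter.

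The on-demand comparison and the A-versus-B equivalence test count all treated bleeds whatever the site (SAP 3.3.1.1 and 3.3.2.1), so neither is touched.

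**What to change.** In SAP 3.3, limit 'other' to recorded sites that are neither joint nor soft tissue/muscle. Add an 'unknown/missing' row to every by-location table, and show its count by regimen and segment beside the joint ABR. Readers can then compute shares among known-site bleeds or bound the joint ABR, and can see whether recording differed between regimens. This also brings the SAP into line with protocol 22.5.1.

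The cost is one sentence in the SAP and one row in tables already planned. No new data are needed and no hypothesis test changes.
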